5.3 Paragon stem - Description

The Paragon stem is a bi-planar wedge shaped monoblock stem of Titanium Alloy (Ti6Al4V), with Titanium plasma and/or Hydroxyapatite (HA) coating. The Paragon stem is available in a collared and collarless version and available in both standard and high offset in a range of sizes. The Paragon stem is compatible with Femoral Heads with a 12/14 taper, including the MobiliT acetabular system. The Paragon stem utilises a bi-planar wedge design to provide primary axial stability and a rectangular cross section to provide primary torsional stability. The stem also features a macrostructure design optimised for osseointegration, which provides secondary stability. The stem's surface along with its tapered architecture has been specifically designed to load the

metaphyseal-diaphyseal region, reproducing the natural physiological loading patterns of the femur.

It is available in twelve (12) sizes (1 through 12) in standard and high offset in 130° CCD angle, which allows the surgeon to preserve bone at the osteotomy level which fundamentally allows for a user-friendly stem. The progressive neck lengths allow bone preserving femoral neck resection and the low-profile neck maximises range of motion. The Paragon stem medial compression grooves are designed to resist compression and stem subsidence and the lateral tension grooves are designed to resist tensile force and prevent stem loosening. The device design incorporates a porous coating of Hydroxyapatite (PCHA), developed to resist potential stem subsidence and loosening. The stem has a polished and offset distal tip which provides a reduction in distal stem engagement and a finer insertion of the stem during the procedure.

The Paragon stem is available in either collared or collarless options. The collared stems have the same function and intended use of non-collared stems but provide those surgeons who prefer it, a more definitive reference point relative to the osteotomy line when inserting the stem into the intra-medullary canal of the patient's femur. The addition of the collar on the stem does not alter the indications for use and their selection for use is at the choice of the surgeon.

Figure 4. Paragon stem (collarless (right); collared (left).

5.4 Paragon stem- Indications and Contraindications for use

The Paragon stem is intended to provide increased patient mobility, range of motion, and reduce pain by replacing the damaged hip joint articulation in patients where there is evidence of sufficient sound bone to seat and support the components.

Indications

The indications for Paragon stem as a total hip arthroplasty and as a hip hemiarthroplasty include:

• Degenerative osteoarthritis of the hip.

- Inflammatory arthritis of the hip.
- Secondary arthritis of the hip, such as may follow trauma (e.g. fracture of the femoral neck, or fracture and/or dislocation of the hip or acetabulum), or congenital conditions (e.g. developmental dysplasia of the hip).
- Displaced intracapsular femoral neck fractures where there is a high risk of non-union or avascular necrosis and bone collapse.
- Avascular Necrosis of the femoral head.

In this PMCF study only primary total hip arthroplasty surgeries will be assessed.

Contraindications

- Infection or sepsis or osteomyelitis.
- Insufficient bone structure or quality which may affect the stability of the implant.
- Rapid joint destruction or bone absorption.
- Skeletal immaturity.
- Muscular, ligamentous, neurological, vascular deficiencies or poor skin coverage, which may compromise the affected extremity.
- Alcoholism or the other addictions.
- Sensitivity to the implant materials.
- High levels of physical activity e.g. competitive sports, heavy physical labour.
- Obesity that can produce loads on the prosthesis, which can lead to failure of the fixation of the device or the device itself.

The Paragon Stem System is TGA approved.

5.5 TaperFit stem - Description

The TaperFit Hip Stem is a double tapered, polished, collarless stem designed to be implanted using bone cement. The TaperFit cemented hip system stem is manufactured from high strength stainless steel and is available in five sizes with three offset configurations: 38mm, 45mm and 50mm. The TaperFit cemented hip system stems are supplied with a PMMA centralizer which attaches to the distal part of the stem and acts to centralize the distal stem in the cement mantle and maintain correct stem alignment.

The TaperFit Hip Stem is TGA approved.

Figure 5. TaperFit Hip Stem with centraliser, a CoCr femoral head and Trinity Acetabular Cup. Note: Trinity Acetabular cup shown for illustration purposes only.

5.6 TaperFit stem- Indications and Contraindications for use

The TaperFit cemented hip system is intended for use as a primary replacement for the hip joint, in association with acetabular components, to reduce pain and restore hip function.

Indications

- Femoral neck fracture
- Osteoarthritis
- Rheumatoid and inflammatory arthritis
- Post-traumatic disease effects,
- Avascular necrosis
- Total hip revision.

Contraindications

- Active infection
- Osteoporosis
- Marked bone loss or bone resorption
- Metabolic disorders which may impair bone formation
- Vascular insufficiency
- Muscular atrophy
- Neuromuscular disease

6.0 STUDY POPULATION

Participants will be selected for recruitment into the study from the general population of patients requiring a primary total hip arthroplasty surgery with a dual mobility construct and considered suitable for the cementless MobiliT cup with ECiMa insert with Paragon or TaperFit stem. Participants who do not meet the inclusion criteria or meet any exclusion criteria are excluded from the study participation. Bilateral participants will be included, and each hip will be assigned a specific study ID and the patient will complete separate questionnaires for each treated hip.

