	 Individuals under guardianship. Individuals with any physical or psychological condition which would impair clinical investigation participation. Individual with current hip infection. Any patient pregnant or with plans to become pregnant during the clinical study. Individuals who are already enrolled in other clinical studies.
Study Procedures	 Demographic information including gender, age, BMI. Pre-operative assessment of the affected hip including primary diagnosis, medical history, clinical and radiographic review. Intra-operative information including components details, surgical approach, complications. Harris Hip Score (HHS) – which includes a functional and clinical assessment (encompassing elements for pain and ROM) Preoperative X-rays and post-operative x-rays up to 2 years – assessment of changes in component positioning, presence, and size of radiolucent lines, osteolysis, heterotopic ossifications. Collection of surgery-/ hip-/ devices-related AEs/SAEs during the surgery and postoperatively up to 10 years.
	Patient Reported Outcomes Measures (PROMs): - Oxford Hip Score (OHS) - EQ-5D-5L (including EQ-5D VAS) - Patient's satisfaction using the 4-point Likert-type scale.
Study Visits	Pre-operative Intra-operative Follow up (FU) visits: 0-6 days, 3 months, 1 year, 2, 5, 7 and 10 years. Telephone Interview: 4 and 9 years.

Statistical methods:

It is planned to conduct a yearly data summary of the study status and available data to feed into the Clinical Evaluation process of the study devices.

An interim analysis shall be performed when the data has been collected for the recruited study population at 2 years follow-up. A final analysis shall be performed when the entire study population has completed 10 years follow-up. Ad-hoc interim reports may also be performed upon request to answer regulatory questions and/or if requested by the Investigator(s), in order to improve scientific knowledge or provide data for presentations and publications.

As this is not a hypothesis-testing study, the analysis of the data will be performed in a descriptive way.

Analysis of primary endpoint:

 Percent change and absolute improvement of OHS will be reported at each follow-up visit compared to pre-op and previous visit(s) using a repeated-measures t-test.

Analysis of secondary endpoints:

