7.2 Clinical Assessment and Patient Reported Outcome Measures (PROMs)

The clinical assessment is performed before surgery, at 3 months, 1 year, 2, 5, 7 and 10 years after the surgery. Preoperative assessment is used as baseline values for score improvement.

Harris Hip Score

The Harris Hip Score (HHS) is a disease-specific scoring system originally intended as outcome score after arthroplasty surgeries that include the domains of function, pain, motion, and deformity 16. The HHS is considered a clinical outcome measure. The maximum score of the absolute HHS is 100 points. Pain domain contributes 44 points, function 47, ROM 5 and absence of deformity 4 points. Function is subdivided into gait and activities of daily living. Calculation of the ROM score includes splitting the motion into categories based on utility and then multiplying the degrees of motion with a given index factor. The index scores are then added and multiplied by a factor of 0.05 to obtain the final ROM score. The ROMs of the affected hip/joint will be measured with a standard goniometer.

Oxford Hip Score

Oxford Hip Score (OHS) is a patient-centred questionnaire that is designed to assess functional ability and pain from the patient's perspective. It is a short, twelve-item questionnaire developed for completion by patients undergoing THA and is extensively referenced in the Orthopaedic literature. The OHS has been demonstrated to be highly sensitive to change in patients undergoing primary THA.¹⁷ Each of the 12 questions on the Oxford hip score presents a score decreasing as the reported symptoms increase (ie. become worse). All questions are laid out with response categories denoting least (or no) symptoms being to the left of the page (scoring 4) and those representing greatest severity lying on the right-hand side (scoring 0). This method, when summed, produces overall scores running from 0 to 48 with 48 being the best outcome.

EQ-5D-5L

The EQ-5D-5L essentially consists of 2 pages: the EQ-5D descriptive system and the EQ visual analogue scale (EQ VAS).

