The descriptive system comprises five dimensions: mobility, self-care, usual activities, pain/discomfort and anxiety/depression. Each dimension has 5 levels: no problems, slight problems, moderate problems, severe problems and extreme problems. The patient is asked to indicate his/her health state by ticking the box next to the most appropriate statement in each of the five dimensions. This decision results in a 1-digit number that expresses the level selected for

that dimension. The digits for the five dimensions can be combined into a 5-digit number that describes the patient's health state.

The EQ VAS records the patient's self-rated health on a vertical visual analogue scale from 0-100, where the endpoints are labelled 'The best health you can imagine' and 'The worst health you can imagine', it is requested for the patient to simply mark an X on the scale to indicate today's health and to write the number marked on the scale in the box. The VAS can be used as a quantitative measure of health outcome that reflect the patient's own judgement.

Subject's satisfaction 4-point Likert-type scale

The overall satisfaction of the patients with the result of the surgery will be scored on a 4-point Likert-type scale with response categories consisting of very satisfied (100 points), somewhat satisfied (75 points), somewhat dissatisfied (50 points) and very dissatisfied (25 points)¹⁸. The satisfaction scale will be completed by the participant postoperatively and the first one will represent the baseline for the following visits.

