10.0 STATISTICAL CONSIDERATIONS

10.1 Statistical Methods and Data Analysis

The following describes the statistical analyses foreseen at the time of study planning. Detailed statistical methods will be described in a separate Statistical Analysis Plan (SAP).

Statistical analyses will be performed when data has been collected for the study population at 2 years, 5 years, and 10 years follow-up.

Descriptive statistics will be provided in summary tables according to the type of variable summarised:

- survivorship will be calculated as Kaplan-Meier analysis with 95% confidence interval.
- quantitative variables will be summarized by using n (sample size), arithmetic mean, standard deviation (SD), median, minimum, and maximum, comparing between follow-ups and baseline values (where applicable).
- categorical variables will be summarized by using frequency count and percent distribution. Additional analysis may include comparisons of interest across demographic and baseline characteristics.

The analyses will include:

Analysis of primary endpoint:

- Percent change and absolute improvement of OHS will be reported at each follow-up visit compared to pre-op and previous visit(s) using a repeated-measures t-test.

Analysis of secondary endpoints:

- The survival of the devices will be expressed as crude revision rates and 95% confidence intervals and include listing of details of revision procedures (reason, time to revision, components revised).
- Hip-/ procedure-/ device- related adverse events will be listed and summarized based on the different mechanisms of classification, such as type of event, timing (operative/post-operative), seriousness and relation with the study devices.
- Postoperative HHS compared to pre-op baseline and previous visits. Percent change and absolute improvement will be reported for total scores and/or sub-scores as appropriate.
- Postoperative EQ-5D-5L compared to pre-op baseline and previous visits. Percent change and absolute improvement will be reported for total scores and/or sub-scores (EQ-VAS) as appropriate.
- Patient's satisfaction with the results of the surgery and any change to previous visit.

 The rates and extent of any radiolucent lines, osteolysis and rates of implant loosening will be reported at specified follow-up time points, as assessed by available radiographs.

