10.2 Sample Size

A minimum of 100 hips will be enrolled into the study according to the selection criteria. Based on a repeated-measures t-test, and assuming a mean difference of 22.6 OHS score points (SD 9.8) from pre-operative to 2 years post-operative²⁰, this sample size will be sufficient to demonstrate a two-tailed effect with an alpha of 0.05 and a power >0.90.

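### EQ-5D-5L and EQ VAS rate the whole patient, but the protocol has bilateral patients complete them separately for each treated hip and sets no patient-level rule

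*Protocol*

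**What the plan says.** Protocol section 6.0 admits bilateral participants and states that "each hip will be assigned a specific study ID and the patient will complete separate questionnaires for each treated hip". The rule covers all questionnaires. The Synopsis lists EQ-5D-5L with its VAS among the patient-reported measures, beside the Oxford Hip Score (OHS) and satisfaction, and Table 1 in section 7.6 schedules it before surgery and at every follow-up visit from 3 months to 10 years except the telephone contacts.

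Section 7.2 describes what the instrument measures. For the descriptive system: "The digits for the five dimensions can be combined into a 5-digit number that describes the patient's health state". For the VAS: "The EQ VAS records the patient's self-rated health on a vertical visual analogue scale from 0-100". Neither refers to a hip.

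On analysis, section 7.2 says "Preoperative assessment is used as baseline values for score improvement", and section 10.1 lists "Postoperative EQ-5D-5L compared to pre-op baseline and previous visits" without naming the unit of analysis. Section 10.2 counts hips: "A minimum of 100 hips will be enrolled into the study according to the selection criteria". Section 6.2 asks for consent for each hip joint. No section sets an interval between two operations, excludes staged surgery, or defines one EQ-5D-5L baseline per patient.

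**The concern.** A questionnaire about a joint can be answered once per joint. A question about general health today has one answer per person per day. Applied as written, section 6.0 has two effects, depending on the timing of surgery.

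- **Same-day bilateral surgery.** One health state is entered under two study IDs.
- **Staged surgery.** The second hip's pre-operative EQ-5D-5L is taken after the first replacement has already acted on general health, so that record's change starts from a post-treatment value. The first hip's later follow-up in turn takes in the course of the second operation.

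Quality of life from baseline to 10 years is a stated secondary objective, and section 3.4 feeds the results into the clinical evaluation of the devices. If the summary runs over hip records, the reported change depends partly on how many bilateral patients enrol and when their second hip is done.

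**Working it through.** **The plan's own figure.** Section 10.2 gives a sample size for OHS only: "assuming a mean difference of 22.6 OHS score points (SD 9.8) from pre-operative to 2 years post-operative", two-sided alpha 0.05, power above 0.90, 100 hips. The standardised change is 22.6 / 9.8 = 2.306, so the noncentrality for a paired t-test is 2.306 × √100 = 23.06 and the power is about 1.000. Five pairs already give 0.964. The stated power reproduces, and the handling of EQ-5D-5L does not touch it. No sample-size figure is given for EQ-5D-5L.

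**Inputs for EQ VAS.** The sponsor's French series in section 3.1 moved from 59.4 before surgery to 82.7 at 2.5 years, a gain of g = 82.7 − 59.4 = 23.3. This is an assumed benchmark. Two further quantities are not in the documents and are varied:

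- s, the share of hip records that are second staged hips;
- c, the share of the patient's total gain already present at the second hip's baseline.

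**Staged surgery.** A first or only hip record shows g and a second hip record shows g(1 − c). The mean over records is (1 − s)g + s·g(1 − c) = g(1 − s·c).

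| s | c = 0.5 | c = 1 (extreme) |
|---|---|---|
| 10% | 23.3 × 0.95 = 22.1 | 23.3 × 0.90 = 21.0 |
| 20% | 23.3 × 0.90 = 21.0 | 23.3 × 0.80 = 18.6 |

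If b is the share of patients who are bilateral, s = b/(1 + b), so b = s/(1 − s). Thus s = 10% means 0.10/0.90 = 11% of patients, and s = 20% means 0.20/0.80 = 25%.

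The formula gives bilateral and unilateral patients the same total gain g. If two operations together bring more than g, the first hip's record carries the excess and offsets part of the dilution.

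**Same-day surgery.** Here let s be the share of records that merely repeat another record. The mean change does not shift through duplication alone if bilateral patients gain as much as the others. The variance of a sum with identical pairs gives a design effect of (1 − 2s) + 4s = 1 + 2s. For b = 5, 10, 20 and 30%, s = b/(1 + b) gives design effects of 1.10, 1.18, 1.33 and 1.46. A standard error that treats records as independent is then too small by 1 − 1/√(design effect), about 4, 8, 13 and 17%.

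The two effects are alternatives for any one patient: the first needs staged surgery, the second needs operations on the same day or close together.

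**The case against.** The strongest reply is that the protocol nowhere says EQ-5D-5L is analysed by hip. Section 10.1 names no unit and leaves detail to an SAP that is not shown and could set a patient-level rule. This stands: per-hip completion is explicit, while per-hip analysis is an inference from the hip IDs, the sample size in hips and the baseline rule.

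A reader might infer that the EQ-5D-5L result is beyond repair because its baseline is contaminated. The documents do not support that. The first hip's pre-operative value is a valid patient-level baseline and is collected anyway; only the second staged record is affected. Nor does it follow that a second hip's change measures nothing. It describes what followed that operation in a patient with one hip already replaced, but it is not a change from an untreated baseline.

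The endpoint is also secondary and descriptive. Section 10.1 ties a t-test to OHS and confidence intervals to survival and revision, and plans neither for EQ-5D-5L. The understated standard error therefore matters only if one is reported; the inflated n would appear in any case.

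On size, the figures at full carry-over are extremes. Patients scheduled for a second replacement are unlikely to be at the 2.5-year mean of 82.7. Shares of 11% and 25% staged bilateral patients would have to arise within an expected two-year recruiting phase. The benchmark series is itself counted in surgeries and may already contain second hips. All of this stands, and it is why the result is a range.

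Finally, timing follow-up from the first operation leaves later visits affected by the second, and a contralateral hip replaced outside the study affects EQ-5D-5L in unilateral participants too. The first limit has to be met in the reporting; the second remains.

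What the reply does not remove is the collection rule. It is in the protocol, it makes no exception, and it yields two whole-person answers that may disagree, with no statement of which one counts.

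**Conclusion.** The point holds in a limited form. The per-hip questionnaire rule in section 6.0 does not fit EQ-5D-5L and EQ VAS as section 7.2 describes them. If the summary follows hip records, same-day bilateral patients are counted twice, and second staged hips contribute a baseline already altered by treatment.

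The size cannot be fixed from the documents. Under the stated assumptions, the mean EQ VAS change falls from 23.3 to between 22.1 and 21.0 with 10% second staged hips, and to between 21.0 and 18.6 with 20%. Because gains credited to the first hip may offset some of this, the net effect is uncertain. The matter is confined to a secondary descriptive endpoint; the OHS endpoint and its power are untouched. It is worth correcting because the collection rule runs for ten years and the correction is small.

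**What to change.** In sections 6.0 and 10.1, state that:

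- EQ-5D-5L and EQ VAS are completed once per patient per assessment date and summarised per patient;
- the baseline is the assessment before the first study hip;
- staged bilateral patients are identified, with the dates of both operations, and the change is reported with and without them, or without their visits after the second operation;
- OHS and the other per-hip scores stay by hip.

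The cost is a wording change and an eCRF adjustment, including a link between a patient's two hip IDs if none exists. Bilateral patients fill in fewer forms. The downside is that n for EQ-5D-5L becomes patients rather than hips, and so is smaller than the hip count. Visits after a second operation still mix the effects of both, which is why the second set of results is needed.

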6.1 Selection Criteria

6.1.1 Inclusion Criteria

Participants meeting all the following inclusion criteria will be considered for participation in the study:

- 1. The individual has signed a Patient Informed Consent Form (PICF), specific to this clinical investigation, and approved by the Human Research Ethics Committee.
- 2. Both genders.
- 3. Age \geq 18 years old, maximum age of 85 years old.
- 4. The individual clinically qualifies for a dual mobility total hip arthroplasty surgery with MobiliT ECiMa cup with Paragon or TaperFit stem based on physical examination and medical history and has been scheduled for surgery.
- 5. The individual is willing to comply with the required protocol for follow-up visits.

6.1.2 Exclusion Criteria

Participants will be excluded if they meet any of the following criteria:

- 1. Individuals under guardianship.
- 2. Individuals with any physical or psychological condition which would impair clinical investigation participation.
- 3. Individual with current hip infection.
- 4. Any patient pregnant or with plans to become pregnant during the clinical study.
- 5. Individuals who are already enrolled in other clinical studies.

